7.7 Long term follow-up assessments

Participants that survive >14 days will continue to be followed up in order to determine their date of death (but there will be no other trial-related assessments during this period).

ASSESSMENT	ENTRY TRIAL	DURING TRIAL (4 HOURLY ASSESSMENTS)	END TRIAL
Demographic information	✓		
Regular medication	✓	✓	
As-required medication	✓	✓	
Fluid intake		✓	
Urinary output		✓	
NuDESC score		✓	
m-RASS score		✓	
Presence of audible upper respiratory secretions		✓	
Presence of symptoms		✓	
Adverse effects (CAH)		✓	
Trial outcome			✓
Overall survival			✓

Table 3 – Summary of trial assessments.

7.8 Withdrawal criteria

Participants may withdraw from the trial at any point, and do not have to give a reason for withdrawal. Withdrawal from the trial will not affect the care provided to the participant. Similarly, personal / nominated consultees may withdraw the participant from the trial at any point: personal consultees do not have to give a reason for withdrawal but nominated consultees will be asked to provide a reason for withdrawal. Again, withdrawal from the trial will not affect the care provided to the participant. Participants that withdraw / are withdrawn will continue to be followed up in order to determine their date of death (but there will be no other trial-related assessments during this period).

The CRF will contain a section for detailing participant withdrawal. Participants that are withdrawn from the trial will not be replaced by alternative participants.

The clinical team may stop CAH (or start CAH) if clinically indicated: the clinical team will be asked to provide a reason for stopping (or starting CAH). Stopping (or starting CAH) is not synonymous with withdrawal from the trial, i.e., the participant assessments will continue until the end of the trial. (The statistical analysis will be undertaken on an intention-to-treat basis).

7.12 End of trial

The end of trial occurs when an individual participant either: a) survives for ≥ 14 days; b) dies (expected outcome); or c) is withdrawn from the trial. The end of trial occurs when the final participant reaches the end of trial (see above).

8 TRIAL TREATMENTS

The health technology being assessed is clinically-assisted hydration (CAH), i.e., parenteral fluids (intravenous/subcutaneous fluids). Currently, there is no agreed “standard of care”, with some patients receiving CAH during the last days of life, whilst other patients do not receive CAH during the last days of life (but receive oral fluids, and/or regular “mouth care”). Moreover, some patients have CAH withdrawn during the last days of life.

Research sites will be randomised to either “standard intervention A” or “standard intervention B” (see below), and this will become the standard of care at the research site for the duration of this trial. The interventions represent the current typical standards of care in the UK.

8.1 Standard intervention A

Standard intervention A involves:

- ❖ Continuance of oral intake (if appropriate) - includes assistance with drinking as required.
- ❖ Regular “mouth care” - mouth care should be performed at least every four hours and should correspond to the research site’s usual procedures for oral care in the terminal phase. Mouth care should be undertaken by the clinical team (but can involve carers if deemed appropriate). Mouth care should be discontinued/withheld if it causes distress/discomfort to the participant or is otherwise difficult to undertake.
- ❖ Standard management of pain and other end-of-life symptoms/problems - should correspond to the research site’s usual procedures for managing relevant problems in the terminal phase.

8.2 Standard intervention B

Standard intervention B involves:

- ❖ Continuance of oral intake (if appropriate) - see above (Standard intervention A).
- ❖ Regular mouth care - see above (Standard intervention A).
- ❖ Standard management of pain and other end-of-life symptoms/problems - see above (Standard intervention A).
- ❖ CAH - see below.

The parenteral fluids may be given either intravenously (if an intravenous cannula is present), or subcutaneously (if no intravenous cannula is present). Intravenous fluids must be administered using an infusion pump, and subcutaneous fluids must be administered using gravity (and not using an infusion pump). The type/volume of fluid administered is based upon relevant NICE guidance [13]: the fluid to be given is dextrose saline (4% dextrose, 0.18% sodium chloride), and the volume to be given is dependent on the participant's weight (Table 4). It should be noted that the volume of fluid is based on a figure of 25 ml/kg/day, which is the lower limit for generic participants, and the upper limit (for consideration) in "old" or "frail" participants [13]. If a recent weight is unavailable, and weighing the participant is problematic, then the clinical team may estimate the current weight.

Participant's weight	Volume of fluid
≤ 40 kg	1 L
50 kg	1.25 L
60 kg	1.5 L
70 kg	1.75 L
≥ 80 kg	2 L

Table 4 - Volume of fluid to be administered [13].

Intravenous fluids should be administered according to the research site's usual procedures. Subcutaneous fluids should be administered according to the following guidelines:

- ❖ Site of cannula - the preferred cannula sites are the lower lateral abdomen, and the upper lateral chest (rather than the upper arm, or the upper leg). If the cannula needs to be changed, then an alternative site should be used.
- ❖ Type of cannula - the preferred cannula is a 24 g BD Saf-T-Intima cannula.

- ❖ Rationale for changing cannula - the decision to change/re-site a cannula is at the discretion of the clinical team. Minimal (asymptomatic) swelling is expected at the site of the cannula and is not in itself a reason to discontinue the infusion and/or re-site the cannula.
- ❖ Rate of infusion - the preferred method of infusion is continuous infusion with the drop rate calculated in the usual manner [39].

Participants with unstable diabetes mellitus may require monitoring of blood sugars (at the discretion of the clinical team). Participants with persistently high blood sugars may require use of other fluids (at the discretion of the clinical team).

8.3 Discontinuation of CAH

The decision to discontinue the CAH is at the discretion of the clinical team (rather than the research team). The CAH should be discontinued if the participant develops clinically significant adverse effects (relating to the CAH), or the participant / personal consultee requests discontinuation.

Minimal (asymptomatic) swelling is expected at the site of the cannula and is not in itself a reason to discontinue the infusion. If the swelling is moderate, then the cannula should be re-sited elsewhere (not the same area). Similarly, if the infusion is not running, or the site of the cannula is inflamed, then the cannula should be re-sited elsewhere.

The development of audible upper airways secretions ("death rattle") is also not in itself an indication to discontinue the infusion, since the development of this problem is independent of hydration status / use of CAH [40,41]. The development of clinically significant (as determined by the clinical team) peripheral oedema, and / or pulmonary oedema is an indication for discontinuation. However, mild peripheral oedema is not in itself an indication to discontinue the infusion. Thus, peripheral oedema is a common problem in patients at the end-of-life and is usually not related to "over hydration".

8.4 Regulatory status of fluid

Dextrose saline is not deemed a drug, and the Medicines and Healthcare products Regulatory Agency (MHRA) have agreed that the trial is not a Clinical Trial of Investigational Medicinal Product (CTIMP) (and does not require a Clinical Trial Authorisation (CTA)).

8.5 Fluid supply and storage

The dextrose saline will be obtained through the trial site's normal medical supplier. The dextrose saline will be stored in the normal manner (no special conditions).

8.6 Assessment of compliance with protocol

The clinical team will record the volume of fluid prescribed, and also the amount of fluid received, in the clinical observation document. The research team will monitor the amount of fluid received and liaise with the clinical team about remedial measures if the volume of fluid received is less than the volume of fluid prescribed (i.e., < 75% total). Compliance with fluid prescription will be documented in the final trial report.

The research team will also monitor the clinical observation chart and liaise with the clinical team about remedial measures if the recording of observations is < 90% total. [In the feasibility trial, the recording of observations was 93.6%] [9]. Compliance with clinical observations will be documented in the final trial report.

9 PHARMACOVIGILANCE

9.1 Definitions

Term	Definition
Adverse Event (AE)	Any untoward medical occurrence in a participant to whom a medicinal product or intervention has been administered, including occurrences which are not necessarily caused by or related to that product.
Serious Adverse Event (SAE)	A serious adverse event is any untoward medical occurrence that: 
• results in death• is life-threatening• requires inpatient hospitalisation or prolongation of existing hospitalisation• results in persistent or significant disability/incapacity• consists of a congenital anomaly or birth defect Other 'important medical events' may also be considered serious if they jeopardise the participant or require an intervention to prevent one of the above consequences. NOTE: The term "life-threatening" in the definition of "serious" refers to an event in which the participant was at risk of death at the time of the event; it does not refer to an event which hypothetically might have caused death if it were more severe.

9.2 Operational definitions for AEs and SAEs

As the trial is being undertaken in participants in the last days of life, progression of existing problems, and development of typical end-of-life problems (e.g., delirium, audible upper airway secretions) are not considered to be AEs / SAEs (and so are not reportable). Similarly, death related to the primary disease / complication of the primary disease is not considered an SAE, nor is inpatient hospitalisation or prolongation of existing hospitalisation, because all participants will already be in a hospital or hospice.

The development of localised swelling at the site of infusion, or the requirement to re-site the cannulae are not considered AEs (and so are not reportable). Other complications of the CAH (e.g., peripheral oedema, pulmonary oedema) will be considered as AEs / SAEs (and so are reportable). Death directly related to the CAH is considered an SAE.

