Thus, there has been a need for further research for some time, but recent events (and the resultant change in clinical practice despite no change in research evidence) has intensified the need for a robust (adequately powered) trial of CAH at the end-of-life. Moreover, the successful completion of the CHELsea I trial [9], which achieved all of its predetermined criteria for success, supports the undertaking of such a trial (utilising a cluster randomised trial design).

The trial will also facilitate the Consortium for Hospice and Community Research (which includes the NIHR) objective to increase the number of hospices recruiting to NIHR CRN portfolio studies [22]. Thus, the trial will recruit 1600 patients from 80 sites within the UK (predominantly inpatient hospices).

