7.5 Baseline data

Baseline data will be collected to describe the trial population (so that comparisons can be made with other populations):

- a) Age
- b) Sex – female, male

- c) Ethnicity
- d) Primary diagnosis – cancer, non-malignant (with specific diagnosis)
- e) Site of care – hospital, hospice
- f) Home-country – England, Northern Ireland, Scotland, Wales
- g) Type of consent – participant, personal consultee, nominated consultee

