9.3 Recording and reporting of SAEs

All AEs will be recorded in the CRF, and SAEs must be reported to Surrey CTU, acting on behalf of the Sponsor, within 24 hours. AEs / SAEs recording starts from the time the participant consents to take part in the trial. AEs will continue to be recorded / reported until the end of the trial (i.e., ≤ 14 days).

The following information will be collected about SAEs (on a specific form): a) full details in medical terms and case description; b) event duration (start and end dates, if applicable); c) action taken d) outcome e) seriousness criteria f) causality (i.e., relatedness to intervention), in the opinion of the investigator; g) whether the event would be considered anticipated. AEs will be followed up until resolved or a final outcome has occurred.

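### Section 9.2 drops hospitalisation and prolonged stay as grounds for SAE status whatever the cause, so a CAH complication leading to either is an SAE only if it meets another criterion

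*Protocol*

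**What the plan says.** Section 9.1 gives the general definition of a serious adverse event. One of its criteria is that the event "requires inpatient hospitalisation or prolongation of existing hospitalisation". It attaches no condition about cause. It also has a discretionary clause for other important medical events.

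Section 9.2 narrows this for a population in the last days of life. Its first paragraph says that "death related to the primary disease / complication of the primary disease is not considered an SAE", and continues: "nor is inpatient hospitalisation or prolongation of existing hospitalisation, because all participants will already be in a hospital or hospice". Its second paragraph turns to the intervention. Local swelling and re-siting of the cannula are not AEs. Then: "Other complications of the CAH (e.g., peripheral oedema, pulmonary oedema) will be considered as AEs / SAEs (and so are reportable". And: "Death directly related to the CAH is considered an SAE".

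Section 9.3 sets out what SAE status brings. All AEs go in the CRF, but "SAEs must be reported to Surrey CTU, acting on behalf of the Sponsor, within 24 hours", with a dedicated form covering seriousness, causality and whether the event was anticipated. Under section 9.4 the principal investigator assigns seriousness by medical judgement.

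On setting, section 2 states that "the trial will recruit 1600 patients from 80 sites within the UK (predominantly inpatient hospices". Section 7.5 records "Site of care – hospital, hospice" as a baseline item, and section 7.3 stratifies the randomisation on the same distinction.

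**The concern.** The two exemptions in one sentence of 9.2 are built differently. Death is exempt by cause. Hospitalisation and prolongation are exempt by setting, on the ground that everyone is an inpatient already. An exemption by setting also covers events caused by the intervention under test, and 9.2 restores only death from that group.

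Tolerability of CAH is a secondary objective (section 3), and the protocol classes the trial as relatively high risk (section 12.1). What is at stake is whether a CAH complication bad enough to move a hospice patient to an acute hospital, or to lengthen a stay, is counted and handled as serious. These events follow exposure to CAH, so any under-classification would fall mainly on the arm that receives it.

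**Working it through.** No figure in the protocol is involved, so there is nothing to recompute. The check sets the provisions side by side.

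**Step 1. Apply 9.1 and 9.2 to four kinds of event.**

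| Event | Under 9.1 | Under 9.2 as worded |
|---|---|---|
| Death from the primary disease or its complication | Serious | Exempt, limited by cause |
| Death directly related to CAH | Serious | SAE, expressly restored |
| Hospitalisation or prolongation due to the primary disease | Serious | Exempt |
| Hospitalisation or prolongation due to a CAH or cannula complication | Serious | Exempt on this ground; nothing restores it |

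The first three rows fit the evident purpose, which is to keep expected end-of-life events out of SAE reporting. The fourth does not.

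**Step 2. Test the stated reason.** The reason is that participants are already in a hospital or hospice.

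- Transfer: most sites are hospices, and the protocol treats hospice and hospital as different settings (sections 5, 7.3 and 7.5). For a hospice inpatient, a move to an acute hospital is a new admission. Being in a hospice beforehand does not make it otherwise.
- Prolongation: this presupposes an existing stay. Already being an inpatient is the condition for the criterion to apply, so it cannot be the reason to drop it.
- Entry criteria: exclusion (i) in section 6.2 concerns patients expected at entry to move elsewhere for end-of-life care. It does not rule out a later, unforeseen transfer for a complication.

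**Step 3. Trace the classification.** Take a hospice participant transferred because of a CAH complication.

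- The event is an AE and goes in the CRF (9.2, 9.3).
- It is not an SAE by reason of the transfer (9.2).
- It is an SAE if it is fatal and directly related to CAH, life-threatening or disabling, or if the investigator chooses to use the important-medical-events clause (9.1).
- If none of these applies, there is no 24-hour report and no SAE form (9.3), and the event is outside the chief investigator's review and coding of SAEs (9.4).

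The second paragraph of 9.2 does not close the gap. It says CAH complications are AEs or SAEs, but not which criterion turns one into the other.

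**The case against.** The strongest reply is that 9.2 should be read as a whole. Its first paragraph opens with the last-days-of-life setting and deals with disease progression and expected problems. The sentence on death and hospitalisation is joined to it by a word of comparison. The second paragraph then deals with CAH separately and names pulmonary oedema. On this reading the hospitalisation exemption never reached CAH complications. The reading is possible but weaker: the limit to primary disease attaches grammatically to death alone, and the reason given for hospitalisation is setting, which is independent of cause. If both readings are open, 80 sites may classify the same event differently, and that also calls for clarification.

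Other points on that side stand and limit the concern:

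- CAH adverse effects are a named secondary endpoint (3.2), assessed every four hours (7.6). A reader might infer that these complications go unreported. They do not.
- A reader might also infer that signals reach the oversight committees late. The documents do not show this: under 9.4 the trials unit collects both AEs and SAEs, and it passes on safety information without limiting it to SAEs.
- An event grave enough to move a dying patient will often meet another seriousness criterion.
- The effect is not strictly confined to one arm, because section 7.8 allows the clinical team to start CAH where clinically indicated, including at control sites.
- With an estimated prognosis of one week or less, transfers and prolonged stays are likely to be uncommon.
- The content of the Appendix 3 flow chart was not visible in the text reviewed, and the Trial Monitoring Plan is a separate document. Either may give handling instructions, but neither would remove the conflict in wording between 9.1 and 9.2.

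**Conclusion.** The concern holds as a conflict of wording with a limited consequence. Section 9.2 removes hospitalisation and prolongation as seriousness criteria for every cause, the reason given does not support that for CAH-related events, and only CAH-related death is restored. The result is possible under-classification of serious CAH-related harm: such an event keeps its place in the AE data but may miss the 24-hour report and SAE form.

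The size cannot be estimated from the protocol. A reader might attach a rate to it. With 1,600 participants and sites randomised 1:1, the CAH arm has about 1600/2 = 800. An assumed rate of 0.25% to 1% would give 800 × 0.0025 = 2 to 800 × 0.01 = 8 affected events. If none were captured, zero serious events in 800 would carry a 95% upper limit of about 3/800 = 0.375%. That rate has no anchor in the documents, and the zero count requires that every event miss every other criterion and that no other SAE occurs. It shows a worst case and is not an estimate, and the finding does not depend on it.

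The conclusion assumes that the sentence means what it literally says and that no other trial document overrides it. It is a cheap correction worth making, and it does not threaten the trial.

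**What to change.** Reconcile 9.1 and 9.2 by limiting the hospitalisation exemption by cause, as 9.2 already does for death. For example: hospitalisation or prolongation related to the primary disease, its complications or end-of-life care is not an SAE; hospitalisation (including transfer from a hospice to an acute hospital) or prolongation attributed to a complication of CAH or its cannula remains an SAE and is reported as section 9.3 requires. Carry the same wording into the SAE guidance for sites, and check that the Appendix 3 flow chart agrees.

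The cost is one sentence, the matching guidance, and probably a few more SAE forms. It needs no extra assessments or staff, and no treatment rule changes.

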3.2 Secondary endpoints/outcomes

The secondary endpoints are:

- ❖ Proportion of participants with Nu-DESC total score of > 0 at any point during the trial.
- ❖ Nu-DESC scores during trial (mean score during the trial; proportion time with score 0; proportion time with score > 0; proportion of time with score > 1).
- ❖ Time to first episode of Nu-DESC score > 1.
- ❖ Proportion of participants that receive as-required and/or regular medication specifically for delirium at any point during the trial (data derived from drug chart).

- ❖ Time to first dose of medication for delirium (as-required or regular – data derived from drug chart).
- ❖ Modified Richmond Agitation and Sedation Scale (m-RASS) scores during trial (mean score during the trial; proportion time with score 0; proportion time with score 0 to -2 – data derived from clinical observation document). The RASS is a validated measuring tool for severity of agitation and level of sedation, and the m-RASS has been modified for/validated in patients with advanced cancer (Table 2) [27].
- ❖ Proportion of participants with audible upper airway secretions at any point during the trial (“death rattle” – data derived from clinical observation document).
- ❖ Time to first episode of audible upper airway secretions.
- ❖ Proportion of participants that receive as-required and/or regular medication specifically for audible upper airway secretions at any point during the trial (data derived from drug chart).
- ❖ Time to first dose of medication for audible upper airway secretions (as-required or regular – data derived from drug chart).
- ❖ Proportion of participants that experience pain, shortness of breath, and nausea and vomiting (and require medication for these symptoms – data derived from clinical observation document and drug chart).
- ❖ Adverse effects of CAH, e.g., peripheral oedema, pulmonary oedema, cannula site inflammation, cannula site infection. (Data derived from clinical observation document)
- ❖ Overall survival (data derived from clinical observation document). Participants that survive >14 days will continue to be followed up in order to determine their date of death.
- ❖ Participant level costs (data derived from clinical observation document and drug chart) and cost effectiveness based on reductions in the likelihood of delirium.

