7.6 Trial assessments

The trial lasts for 14 days (maximum). However, it is expected that the majority of participants will have died within this time period (of their primary disease).

Participants will be reviewed every four hours during the trial by the clinical team, and the following assessments completed (by the clinical team):

- ❖ Nu-DESC score (see above)
- ❖ m-RASS score (see above)
- ❖ Presence of audible upper airway secretions (“death rattle”)
- ❖ Presence of pain – patient reported
- ❖ Presence of shortness of breath – patient reported
- ❖ Presence of nausea and vomiting – patient reported (nausea and vomiting), or nurse assessment (vomiting)
- ❖ Presence of adverse effects of CAH (see above)

The clinical team will also record the participant's fluid intake (oral, CAH), and medications / other interventions provided to the participant (and the indications) during the trial.

Data on usage of CAH paraphernalia (e.g., cannulae, giving sets), and paraphernalia relating to other interventions will also be recorded (to support the health economic analysis).

Overall survival (from the time of randomisation) will be recorded. [Participants that survive >14 days will continue to be followed up in order to determine their date of death].

The clinical team will complete a trial-specific clinical observation document, which will be transcribed by the research team into the case report form (CRF). The research team will also use the participant's clinical notes and drug charts as source documents.

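### Oedema is recorded only under a label that attributes it to CAH and without an entry assessment, so new oedema cannot be reliably told from old and the arms may be recorded differently

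*Protocol*

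**What the plan says.** Tolerability of CAH is secondary objective (c) in section 3. Section 3.2 lists the endpoint as "Adverse effects of CAH, e.g., peripheral oedema, pulmonary oedema, cannula site inflammation, cannula site infection". In section 7.6, "Participants will be reviewed every four hours during the trial by the clinical team, and the following assessments completed"; one item is "Presence of adverse effects of CAH (see above"). The item asks about presence, not onset or worsening.

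Table 3 (section 7.7) labels the row "Adverse effects (CAH") and gives it a single tick, which reads as the during-trial column. Section 7.5 opens "Baseline data will be collected to describe the trial population" and lists age, sex, ethnicity, diagnosis, site of care, home country and type of consent. Oedema is not in that list.

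Three statements bear on reportability:

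- Section 9.2 exempts "progression of existing problems, and development of typical end-of-life problems" from AE and SAE reporting, with delirium and airway secretions as examples.
- Section 9.2 then says "Other complications of the CAH (e.g., peripheral oedema, pulmonary oedema) will be considered as AEs / SAEs (and so are reportable").
- Section 8.3, on stopping CAH, says "peripheral oedema is a common problem in patients at the end-of-life and is usually not related to" over-hydration.

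**The concern.** A harm measure that is compared between arms should be defined without reference to which treatment caused it. Here the label asks the nurse to judge attribution while knowing the allocation. At an intervention A site there is normally no CAH to attribute oedema to. At an intervention B site there is, but section 8.3 tells staff that peripheral oedema usually has another cause. Each site has one allocation, so a site's habit in reading the label cannot be separated from its arm.

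The missing entry record adds a second problem. Delirium and airway secretions in the previous 24 hours are exclusions (section 6.2, g and h), so those outcomes are new when they occur. Oedema has no such exclusion. Section 6.2 also admits patients at B sites who are already receiving CAH, so the first four-hourly review cannot serve them as a pre-CAH baseline.

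At stake is the main systemic harm to be set against any benefit on delirium. The other harms named in section 3.2 are cannula-site events.

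**Working it through.** **Reading the sections together**

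1. *Who is assessed.* Section 7.6 applies the four-hourly item to participants generally, and Table 3 is not split by arm. Unequal recording is therefore not prescribed.
2. *How the item is completed without CAH.* No section says. Section 9.1 ties an AE to an administered product or intervention without requiring causality. Section 8.1 calls the comparator Standard intervention A, so whether oedema in that arm qualifies can be read either way.
3. *Existing oedema.* The four-hourly presence item could count it. The first sentence of 9.2 excludes it from AE reporting. Without an entry record, staff cannot tell which case they have.
4. *New peripheral oedema.* The complications sentence in 9.2 makes it reportable. The typical-problems sentence, read with 8.3, suggests that it is not. Section 8.3 calls only peripheral oedema common, so this conflict does not extend to pulmonary oedema.

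**Illustration of size**

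The protocol states no oedema rate, so there is no figure to reproduce. All rates below are assumptions.

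*(a) Equal recording, no entry status.* Let q be the proportion with oedema at entry (the same in both arms), with new oedema in 5% (A) and 10% (B) of the remainder. Recorded proportion = q + (1 − q) × new-onset risk.

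- q = 0.30: A = 0.30 + 0.70 × 0.05 = 33.5%; B = 0.30 + 0.70 × 0.10 = 37.0%. Difference 3.5 points, risk ratio 0.370/0.335 = 1.10.
- q = 0.20: 24.0% v 28.0%, difference 4.0 points, risk ratio 1.17.
- q = 0.40: 43.0% v 46.0%, difference 3.0 points, risk ratio 1.07.

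The true excess of new oedema among all randomised is (1 − q) × (10% − 5%). At q = 0.30 this is 0.70 × 5 = 3.5 points, equal to the recorded difference, so that difference is unbiased. Among those free of oedema at entry the risk ratio is 2.0.

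Precision does suffer. Evaluable participants per arm = 1600 × 0.95 / 2 = 760. Section 10.1 gives a design effect of 1.475 (1 + 19 × 0.025) for delirium; borrowing it for oedema is a further assumption. Effective size = 760 / 1.475 ≈ 515 per arm.

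- Any presence, 33.5% v 37.0%: SE = √[(0.335 × 0.665 + 0.370 × 0.630)/515] ≈ 3.0 points; power at two-sided 5% about 22%.
- New oedema only, 3.5% v 7.0% of all randomised: SE = √[(0.035 × 0.965 + 0.070 × 0.930)/515] ≈ 1.4 points; power about 71%.

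The same 3.5-point effect has roughly twice the standard error when existing oedema is left in.

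*(b) Unequal recording, no true effect.* Let 30% have oedema present in both arms, fully recorded in B, with A recording a fraction s. False excess = 30% × (1 − s).

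- s = 0.90: 3 points.
- s = 0.75: 30.0% − 22.5% = 7.5 points.
- s = 0.50: 15 points.

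At the same effective size, s = 0.75 would be declared significant in about 78% of trials. Under-recording in B by the same fraction would produce a false deficit.

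**The case against.** The best defence is that section 7.6 schedules the item for everyone. A reader might infer from the label that A sites record nothing, but no section says so, and any scenario built on that is an extreme without support. A participant in arm A may also be started on CAH (section 7.8). This part of the defence stands, so unequal recording must be put as a risk.

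A reader might also infer that the excess due to CAH cannot be estimated at all. The arithmetic above shows otherwise: with equal recording and equal entry prevalence, the randomised risk difference is unbiased. That stands too. The loss is in precision, in the risk ratio and in the ability to see worsening.

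Third, it is tempting to say that pre-existing oedema counts as an adverse event. Section 9.2 exempts progression of existing problems, so this can be said only of the four-hourly presence item. The sentence naming oedema could also be read as the specific rule that overrides the general one, and 8.3 governs stopping CAH, not recording. Both are fair readings, but the protocol does not choose between them.

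Finally, the observation document is not shown and may list oedema neutrally. Excluding clinically significant cardiac and renal failure probably lowers entry prevalence. Serial four-hourly data give an early first observation, and causality is already collected for SAEs (section 9.3). These points mitigate the problem. They do not supply an entry record, and an analysis plan cannot recover a status that was never collected.

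**Conclusion.** The point holds as a weakness in outcome definition and ascertainment. Three things are established from the text: oedema is captured only by attribution to CAH, no entry assessment is scheduled, and the reporting rule for peripheral oedema is unresolved between sections 8.3 and 9.2. Differential recording by arm is a well-founded risk because the trial is unblinded and sites carry a single allocation. Its direction is not fixed.

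The size depends entirely on assumed rates. At 30% entry prevalence and 5% v 10% new onset, equal recording leaves the 3.5-point difference intact but takes the risk ratio from 2.0 to 1.10 and about doubles the standard error. A 25% shortfall in recording at A sites, on a true 30% in both arms, would create a false excess of 7.5 points. The change is worth making because it is cheap and the information cannot be recovered later. The primary outcome is not affected.

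**What to change.** - In sections 3.2 and 7.6 and in Table 3, replace the attributed label for oedema with two neutral observations, peripheral oedema and clinical signs of pulmonary oedema. Record them at entry and at each four-hourly review in both arms, with enough grading to show worsening.
- Define the endpoint as new or worsened oedema, compared by randomised arm.
- Keep cannula-site events as CAH-specific.
- Record causality in a separate field.
- Reconcile sections 8.3 and 9.2 so that one reporting rule for oedema applies in both arms. This concerns recording only; the criteria for stopping CAH are for the clinical investigators and are not addressed here.

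The cost is one added entry record, a relabelled row on the observation document, some extra work for sites in grading, and somewhat more non-serious AE entries from A sites.
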